#### 18.2.3. ANALYSIS OF SECONDARY EFFICACY VARIABLES

For the continuous secondary efficacy endpoints, percent change in AAPS from baseline to Week 12 and change in number of pain free days per week from baseline to Week 12, the same methodology used for the primary efficacy endpoint will be used for the analysis. The analyses for percent change in AAPS from baseline at Week 12 will include both evaluation at the scheduled visit for Week 12 (Visit 8) and Week 12 based on baseline day as described in Section 18.1.3. The analyses for change in number of pain free days per week from baseline at Week 12 above will include the evaluation at Week 12 based on baseline day as described in Section 18.1.3.

For the binary secondary efficacy endpoints (proportion of subjects with a  $\geq$  30%,  $\geq$  40%, and  $\geq$  50% improvement in AAPS from baseline to Week 12 and proportion of subjects achieving a  $\geq$  30%,  $\geq$  40%, and  $\geq$  50% improvement in AAPS from baseline for at least 6 of the 12 weeks during the Main Study Treatment Period), a CMH test will be conducted to compare placebo against each of the olorinab treatments (10 mg, 25 mg, 50 mg, pooled 25 and 50 mg, and olorinab pooled), stratified by the randomization factor (sex and IBS

subtype). The responder rate and the odds ratio relative to placebo will be presented with corresponding CIs, and the percentage of difference from placebo will be presented together with corresponding 95% CIs and the p-values. The 95% CI for the responder rate of each treatment group will be generated using the normal approximation method. Missing data will be imputed using MI, as described in Section 18.2.2.

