### 8.3. Statistical Analyses

Details regarding the statistical analyses will be provided in the SAPs. The SAP for the Main Study will be finalized prior to database lock (unblinding) of the Main Study and the SAP for the LTE will be finalized prior to database lock for the LTE. Results of the Main Study and the LTE may be reported in 2 separate clinical study reports.

Continuous variables will be summarized using the number of observations, mean, SD, median, minimum, and maximum. Categorical variables will be summarized using frequency counts and percentages. For time-to-event variables, the number of subjects at risk over time, as well as the cumulative percentage of subjects experiencing the event of interest will be presented, based on Kaplan-Meier methodology.

Unless otherwise specified, continuous endpoints will be analyzed using a mixed-effects model repeated measures (MMRM) analysis with treatment, the stratification factors, visit, and treatment-by-visit interaction as factors and Baseline AAPS and Baseline value (if applicable) as covariates. Visit will include all scheduled visits except Visit 9 (Week 14). Least squares means, standard errors (SEs), and 95% confidence intervals (CIs) for the treatments and their difference will be presented together with the p-values.

Continuous endpoints derived from the eDiary (eg, score in abdominal pain, bloating, discomfort, number of bowel movements), will be analyzed using the MMRM above that includes scheduled visit, as well as a second MMRM model that includes treatment, the stratification factors, week, and treatment-by-week interaction as factors and Baseline AAPS and Baseline value (if applicable) as covariates. Week will include each week from Week 1 to Week 12. Least squares means, standard errors (SEs), and 95% confidence intervals (CIs) for the treatments and their difference will be presented together with the p-values.

Categorical endpoints will be analyzed by either the Cochran-Mantel-Haenszel (CMH) method, Fisher's exact test, or by logistic regression with a model that includes treatment and stratification factors as factors and Baseline AAPS and Baseline value (if applicable) as covariates. The odds ratio relative to placebo and percentage of difference from placebo will be presented together with corresponding 95% CIs and the p-values.

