#### **Exploratory**

## **8.3.1.2.** Long-Term Extension Endpoints

## **Primary**

## **8.3.2.** Main Study Efficacy Analyses

Statistical analysis methods for efficacy analyses in the Main Study are listed in Table 6.

**Table 6:** Statistical Analysis Methods for Efficacy Analyses

Endpoint	Statistical Analysis Methods
Primary	The primary endpoint, change in AAPS from Baseline to Week 12, will be analyzed using a MMRM analysis with treatment, stratification factors, visit, and treatment-by-visit interaction as factors and Baseline AAPS as a covariate. An unstructured variance-covariance matrix will be used for the MMRM analysis. Least squares means, SEs, and 95% CIs for the treatments and their difference will be presented together with the p-values.  The primary analysis will be conducted in the FAS. Sensitivity analyses will be detailed in the SAP.
Secondary	The proportion of subjects achieving a ≥ 30% improvement in AAPS from Baseline to Week 12 will be analyzed using the CMH test stratified by the stratification factors. The odds ratio relative to placebo and percentage of difference from placebo will be presented together with corresponding 95% CIs and the p-values.
	The proportion of subjects achieving a $\geq 30\%$ improvement in AAPS for at least 6 of the 12 weeks during the Treatment Period will be analyzed using the CMH test stratified by the stratification factors. The odds ratio relative to placebo and percentage of difference from placebo will be presented together with corresponding 95% CIs and the p-values.
	The percent change in AAPS from Baseline to Week 12 and Change from Baseline to Week 12 in number of pain free days will be analyzed using the same MMRM analysis as specified for the primary endpoint above.
	The change and percent change in AAPS from Baseline to Week 12 and change from Baseline to Week 12 in number of pain-free days per week will be analyzed using another MMRM model with treatment, stratification factors, week, and treatment-by-week interaction as factors and Baseline AAPS as a covariate. An unstructured variance-covariance matrix will be used for the MMRM analysis. Least squares means, SEs, and 95% CIs for the treatments and their difference will be presented together with the p-values.
	A detailed description of PK analyses will be provided in the SAP.
	Additional details regarding the statistical methods for secondary endpoints will be described in the SAP.

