#### 9. STATISTICAL CONSIDERATIONS

# 9.1. ADJUSTMENTS FOR COVARIATES AND FACTORS TO BE INCLUDED IN ANALYSES

The following covariates and factors are used in the analyses. For details of their inclusion in the models, see the specific analysis section.

- Baseline AAPS value
- Treatment: (Placebo, Olorinab 10 mg, Olorinab 25 mg, Olorinab 50 mg) and, additionally for primary and secondary efficacy endpoints, (Placebo and Olorinab pooled; Placebo, Olorinab 10 mg, Olorinab 25 and 50 mg pooled)
- Stratification factors:
  - Sex: Male, Female
  - IBS subtype: IBS-C, IBS-D
- Week: Week 1 Week 14
- Scheduled Visit: Day 1, Week 2, Week 4, Week 8, Week 10, Week 12, Week 14
- Treatment-by-week interaction
- Treatment-by-visit interaction

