#### 18.1.3. PRIMARY ANALYSIS OF PRIMARY EFFICACY VARIABLE

The primary efficacy analysis will be performed using the FAS population. The primary efficacy endpoint will be analyzed using a MMRM analysis with treatment group (placebo, olorinab 10 mg, olorinab 25 mg, olorinab 50 mg), stratification factors (sex and IBS subtype), week, and treatment-by-week interaction as factors and baseline AAPS as a covariate. Week will include each week from Week 1 to Week 12 based on eDiary data beginning from Day 1 (Randomization). In addition, two additional MMRMs will be completed with the following treatment groupings: 1) placebo, olorinab 10 mg, and olorinab 25 and 50 mg pooled and 2) placebo and pooled olorinab.

The primary objective of this study is to test the hypothesis that the change in AAPS from baseline to Week 12 is the same across treatment group (placebo, olorinab 10 mg, 25 mg, and 50 mg). The alternative hypothesis is that the change in AAPS from baseline to Week 12 differs between placebo and one of the olorinab treatments (10 mg, 25 mg, or 50 mg) or olorinab 25 mg/50 mg pooled.

Four hypothesis tests for the primary endpoint using the primary analysis methodology

described above are specified below.

- MMRM model with treatment groups (placebo, 10 mg, 25 mg, and 50 mg), and with
   3 pre-specified comparisons of placebo vs. the individual treatment groups of olorinab (10 mg, 25 mg, and 50 mg)
- MMRM with treatment "groups" placebo, 10 mg, and pooled olorinab [25 mg + 50 mg], and with 1 pre-specified comparison of placebo vs. the pooled olorinab group [25 mg + 50 mg]

No multiplicity control is planned for this Phase 2 study. If any of the four pre-specified hypothesis test analyses demonstrates statistical significance at the 0.05 (2-sided) significance level at Week 12, then the study successfully demonstrated that the primary endpoint was met.

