#### 18.2.2. MISSING DATA METHODS FOR SECONDARY EFFICACY VARIABLES

For the continuous endpoint of percent change in AAPS from baseline to Week 12, the MMRM models described in Section 18.1.3 will be used. For the continuous endpoint of change in number of pain free days per week from baseline to Week 12, the by-week MMRM model described in Section 18.1.3 will be used. For the change in number of pain free days per week endpoint, a subject with a missing value for a given day when there are non-missing values during the week will be assumed to not be pain free for that day.

For the binary endpoints of proportion of subjects achieving a  $\geq$  30% improvement in AAPS from baseline to Week 12 and proportion of subjects achieving a  $\geq$  30% improvement in AAPS from baseline for at least 6 of the 12 weeks during the Main Study treatment period, all missing post-baseline AAPS values will be imputed using MI under the MAR assumption as described in Steps 1 and 2 of Section 18.1.4. The following steps will then follow:

- Step 3: Subjects will be classified as responders or non-responders per imputed data based on the endpoint criteria specified in Section 18.2.1 for the endpoint of interest. For each dataset, the proportion of responders and non-responders will be calculated.
- Step 4: The Cochran-Mantel-Haenszel (CMH) test, stratified by sex and IBS subtype, will be run for each of the 100 datasets to obtain 100 odds ratio estimates of interest (active treatment over placebo). Common risk difference estimates, CIs, and two-sided p-values will also be calculated for active treatment minus placebo based on

Mantel-Haenszel weights. For the 100 odds ratio estimates and difference estimates in each treatment, the estimates will be passed directly to PROC MIANALYZE, along with their associated standard errors. In some cases, an odds ratio estimate may be calculated as missing due to a value of zero in the denominator for certain treatment comparisons; the missing value for that imputation cannot be passed to PROC MIANALYZE. As a result there may be fewer than 100 odds ratio estimates used to calculate the pooled estimate in these instances.

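### Change in pain-free days is adjusted for baseline AAPS but not for its own baseline: the protocol is inconsistent on this, and adding the covariate is a cheap, probably modest gain in precision

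*SAP*

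**What the plan says.** SAP 18.2.3 covers the two continuous secondary endpoints, percent change in AAPS and change in pain-free days per week. For both, "the same methodology used for the primary efficacy endpoint will be used for the analysis". For pain-free days, SAP 18.2.2 names the model: "the by-week MMRM model described in Section 18.1.3 will be used". SAP 18.1.3 defines that model with treatment, sex and IBS subtype, then "week, and treatment-by-week interaction as factors and baseline AAPS as a covariate". In the SAP 9.1 list of covariates the only baseline measurement is "Baseline AAPS value". The ANCOVA sensitivity analyses for this endpoint (SAP 18.2.4, by reference to 18.1.4) have the same single baseline covariate.

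The protocol addresses this endpoint's covariates in three places:

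- Protocol 8.3, general paragraph. It opens "Unless otherwise specified, continuous endpoints will be analyzed using a mixed-effects model repeated measures (MMRM) analysis" and adjusts for "Baseline AAPS and Baseline value (if applicable) as covariates".
- Protocol 8.3, next paragraph, on continuous endpoints derived from the eDiary. It sets out a second, by-week MMRM with the same two covariates. This paragraph does not carry the opening qualifier.
- Protocol 8.3.2, Table 6. Percent change in AAPS and change in pain-free days "will be analyzed using the same MMRM analysis as specified for the primary endpoint above". Table 6 then gives both endpoints a by-week MMRM. Baseline AAPS is the only covariate in each model.

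SAP 4.3 reports no changes in analysis from the protocol and does not mention the difference.

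**The concern.** For AAPS endpoints, baseline AAPS is the endpoint's own baseline, and adjusting for it is standard. When the same model is carried over to pain-free days, the covariate becomes a related but different measure, and the endpoint's own starting value is left out. That value is already needed to compute the change score. SAP 7.2 derives baselines for the other continuous diary endpoints in the same manner as for AAPS, from the run-in diary. Neither document says why it is omitted as a covariate.

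At stake is the width of the confidence interval, and how far a chance difference between arms in baseline pain-free days moves the estimate. A secondary objective is to compare change in pain frequency, and pain-free days is the one endpoint visible in the public text that serves it. SAP 9.4 relies on estimates and confidence intervals for secondary endpoints, so interval width is much of what this analysis delivers.

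**Working it through.** **The plan's own figure.** The only power statement concerns AAPS: 60 per group, difference 1.0, SD 1.9, two-sided 0.05, at least 80% power. A two-sample t-test has noncentrality 1.0 / (1.9 × √(2/60)) = 2.88 and power 81.6%, so the statement reproduces. It says nothing about pain-free days, for which the documents give no SD, correlation or power.

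**Inputs (assumed).** All quantities are conditional on baseline AAPS, which is already in the model. Let k = SD of baseline pain-free days / SD of Week 12 pain-free days, and let ρ be their correlation. Set the Week 12 SD to 1.

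**Formulas.**

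- Residual variance of the change score with AAPS only: 1 + k² − 2ρk
- Residual variance with both baselines: 1 − ρ²
- Difference: (1 + k² − 2ρk) − (1 − ρ²) = (k − ρ)². In large samples, adding the covariate therefore cannot widen the interval, and it gains nothing when k = ρ.
- Extra CI width with AAPS only: √[(1 + k² − 2ρk) / (1 − ρ²)] − 1

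**Worked examples.**

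- k = 0.5, ρ = 0.3: 0.95 / 0.91 = 1.044, square root 1.022, so 2.2% wider.
- k = 0.75, ρ = 0.5: 0.8125 / 0.75 = 1.083, square root 1.041, so 4.1% wider.
- k = 1, ρ = 0.5: 1.00 / 0.75 = 1.333, square root 1.155, so 15.5% wider.

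**Extra CI width, AAPS only versus both baselines.**

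| k | ρ = 0.3 | ρ = 0.5 |
|---|---|---|
| 0.2 | 0.5% | 5.8% |
| 0.3 | 0.0% | 2.6% |
| 0.5 | 2.2% | 0.0% |
| 0.75 | 10.6% | 4.1% |
| 1.0 | 24.0% | 15.5% |

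Over a wider assumed grid (k from 0.2 to 1.0, ρ from 0 to 0.7) the range is 0% to 41%. The top is at k = 1, ρ = 0.

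**Check at the trial's size.** A simulated single-time-point ANCOVA with 60 per arm gave these ratios of CI width (AAPS only / both):

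- k = ρ = 0.3: 0.996
- k = ρ = 0.5: 0.995
- k = 0.5, ρ = 0.3: 1.018
- k = 0.75, ρ = 0.5: 1.036
- k = 1, ρ = 0.5: 1.149
- k = 1, ρ = 0.3: 1.237

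In these runs the worst cost of adding the covariate was about 0.5% of CI width.

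**In terms of power.** If the AAPS-only analysis had 80% power, adding the covariate would give about 82% at k = 0.5, ρ = 0.3; 83% at k = 0.75, ρ = 0.5; and 90% at k = 1, ρ = 0.5.

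**Which part of the range is likely.** Randomization requires a run-in AAPS of at least 4 (Protocol 3.5), so baseline pain-free days may be few and vary little. The baseline also draws on 14 to 19 days, against 7 at Week 12. Both point to k well below 1. This is inference, not a figure in the documents.

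**The case against.** The strongest reply is that the SAP breaks no rule. The general paragraph of Protocol 8.3 is a default that gives way to specific text, and Table 6 names this endpoint with baseline AAPS as the only covariate. That stands. A reader might infer that the SAP discards a covariate the protocol requires, but the documents do not support this: the choice originates in Table 6 and the SAP follows it. What survives is an inconsistency within the protocol, because the eDiary paragraph of 8.3 has no such qualifier and lists both covariates for the same by-week model.

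A reader might also infer bias through regression to the mean. That does not follow. Regression to the mean acts on all randomized arms alike in expectation, and the standard error already allows for chance imbalance. Nor is the change score unadjusted: baseline AAPS, sex and IBS subtype are in the model.

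The stakes are also limited. Secondary endpoints are exploratory with no formal testing, and the success rule in SAP 18.1.3 depends on AAPS alone. This lowers the priority of the point without removing it.

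Finally, a baseline-by-week interaction would complicate a 12-week unstructured model for which the SAP already plans convergence fallbacks. That is fair, and the gain sought here does not depend on it.

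**Conclusion.** The omission is real as written, and the protocol contradicts itself on it. The consequence is possible loss of precision on one exploratory secondary endpoint, not bias and not a departure from endpoint-specific protocol text. Its size cannot be fixed from the documents. At moderate correlation (0.3 to 0.5) it runs from nil to about 6% of CI width for k of 0.2 to 0.5, and from 4% to 11% at k = 0.75. The 15% to 24% at k = 1 should not be read as the expected loss, since the entry criterion makes equal SDs unlikely.

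These figures rest on assumed k and ρ, on a linear model at Week 12 alone, and on treating a 0-to-7 count as roughly continuous. The example code in SAP Appendix 4 is not shown, so the programmed covariates could not be checked. This is a free improvement in the practical sense: modest expected gain at negligible cost.

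**What to change.** Before unblinding, for change in pain-free days per week:

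- Add baseline pain-free days per week (run-in diary, scaled to 7 days) alongside baseline AAPS in the by-week MMRM, under all three treatment groupings. A baseline-by-week interaction is optional.
- Add it to the matching ANCOVA sensitivity models, observed-case and multiple imputation, and to the imputation regressions so that the two agree.
- Add it to the list in SAP 9.1, and record in SAP 4.3 that the analysis follows the eDiary paragraph of Protocol 8.3 rather than Table 6. If the sponsor prefers Table 6, state why the endpoint's own baseline is left out.

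The cost is a few lines of SAP text and one covariate already collected. Section 4.3 of the long-term extension SAP says that the Main Study analysis has been completed. If so, the adjusted model belongs in the study report as a labelled unplanned analysis under SAP 5.2 (Main Study), beside the planned one.

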## 18.2.4. SENSITIVITY ANALYSIS OF SECONDARY AND KEY EXPLORATORY EFFICACY VARIABLES

The robustness of the secondary endpoints' results will be assessed using various sensitivity analyses. The following analyses will be used:

- For continuous endpoints, the ANCOVA with OC, ANCOVA with MI, and Non-parametric Wilcoxon Rank-Sum Test will be implemented as described in Section 18.1.4.
- For binary endpoints based on AAPS and bowel motility endpoints (including the three composite responder endpoints for IBS-C and IBS-D), the sensitivity to missing data assumptions will be evaluated with the following models:
  - CMH with OC: The CMH test described in the analysis of secondary efficacy variables Section will be repeated on the population of subjects with observed data for the given analysis.
  - o CMH with NRI (non-responder imputation): The CMH test described in the analysis of secondary efficacy analysis Section will be completed on all subjects in the FAS. Subjects will be considered a non-responder if they do not meet the endpoint criteria (e.g. a ≥ 30% improvement in AAPS) or are missing data at the time point of interest. All non-responders at the time point of interest, as well as subjects who discontinue study treatment at any time prior to that time point for any reason, will be defined as non-responders for the analysis. Randomized subjects without at least 1 post-baseline observation will also be defined as non-responders in NRI analyses.
  - o Logistic regression (OC): A logistic regression model using observed cases will be used to analyze treatment comparisons between the proportion of subjects achieving a ≥ 30% improvement in AAPS from baseline to the given time point, with the explanatory variable of treatment (placebo, olorinab 10 mg, olorinab 25 mg, olorinab 50 mg), randomization stratification factor (sex and IBS subtype) and baseline AAPS as a covariate. In addition, two additional logistic regression models will be completed with the following treatment groupings: 1) placebo, olorinab 10 mg, and olorinab 25 and 50 mg pooled and 2) placebo and pooled olorinab. The endpoint of subjects

[figure not shown]
**IIQVIA** 

achieving a  $\geq$  30% improvement in AAPS from baseline for at least 6 of the 12 weeks during the Treatment Period will also be analyzed using the same logistic regression models.

• Sensitivity to analysis set: The secondary analysis will be repeated for the Per Protocol Set.

[figure not shown]
The sensitivity analyses for the composite responder endpoint based on AAPS reduction and no worsening in bowel motility as defined in Section 18.3.8, will be performed using CMH with OC and CMH with NRI in FAS only.

[figure not shown]
Analysis Plan - Main Study

Page 36 of 77

[figure not shown]
Page 37 of 77

Page 38 of 77

[figure not shown]

Page 39 of 77

[figure not shown]
Page 40 of 77

[figure not shown]
Page 41 of 77

[figure not shown]
Page 42 of 77

[figure not shown]
Page 43 of 77

Page 44 of 77

[figure not shown]
Page 45 of 77

Page 46 of 77

[figure not shown]

Page 47 of 77

Page 48 of 77

Page 49 of 77

## 19. SAFETY OUTCOMES

All analyses for safety outcomes will be based on the safety analysis set. All safety data will be listed and summarized by actual treatment group. There will be no statistical comparisons between the treatments for safety data, unless otherwise specified. Unless otherwise stated, treatments displayed will include placebo, olorinab 10 mg, olorinab 25 mg, olorinab 50 mg, olorinab 25 and 50 mg pooled, and pooled olorinab.

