#### **Primary**

- Change in average abdominal pain score (AAPS) from Baseline to Week 12
- Adverse events and clinically relevant changes in vital signs and clinical laboratory results

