#### 8.3.4. Main Study Safety Analyses

All safety analyses will be performed on the Main Study Safety Population. All safety data will be listed and summarized by treatment group. Additional statistical analysis methods for safety analyses are listed below.

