#### 3. STUDY OBJECTIVES

#### 3.1. Primary Objectives

The primary objectives are:

- To compare the efficacy of different doses of olorinab versus placebo on improvement in abdominal pain severity in subjects with irritable bowel syndrome (IBS)
- To compare the safety and tolerability of different doses of olorinab versus placebo in subjects with IBS

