#### 4.3. CHANGES TO ANALYSIS FROM PROTOCOL

There are no changes in analysis or definitions from those planned in the final protocol and no changes required due to COVID-19.

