#### 9.4. MULTIPLE COMPARISONS/ MULTIPLICITY

No formal testing strategy or adjustments of the type I error will be employed for the primary, secondary or exploratory endpoints. Estimates and CIs for treatment groups and from pairwise comparisons will be used in an exploratory manner.

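### Comparing safety with placebo is a primary objective, but the Main Study SAP plans only by-arm safety summaries, so that objective gets no estimate of the difference or of its imprecision

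*SAP*

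**What the plan says.** The safety objective is one of two primary objectives, in the same words in protocol section 2.1 and Main Study SAP section 3.1: "To compare the safety and tolerability of different doses of olorinab versus placebo in subjects with IBS". Protocol section 8.3.1.1 lists a matching item under the primary endpoints: "Adverse events and clinically relevant changes in vital signs and clinical laboratory results".

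The specific safety text is descriptive in both documents. Protocol section 8.3.4: "All safety data will be listed and summarized by treatment group". SAP section 19: "All safety data will be listed and summarized by actual treatment group", followed by "There will be no statistical comparisons between the treatments for safety data, unless otherwise specified". Sections 19.1 to 19.6 then plan counts, percentages, descriptive statistics, shift tables and listings. The displayed groups are placebo, each dose, 25 and 50 mg pooled, and all olorinab pooled.

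Two general passages also bear on the point. SAP section 9.4 disclaims any type I error adjustment and adds: "Estimates and CIs for treatment groups and from pairwise comparisons will be used in an exploratory manner". Protocol section 8.3 says of categorical endpoints: "The odds ratio relative to placebo and percentage of difference from placebo will be presented together with corresponding 95% CIs and the p-values".

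**The concern.** An objective worded as a comparison would normally lead to an estimate of a difference. Here it leads to columns of percentages that the reader must compare by eye. With about 60 subjects per arm, equal or similar percentages can be mistaken for evidence of similar risk when a sizeable excess is still compatible with the data.

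This matters most for the outcomes the protocol itself draws attention to. Protocol sections 1.2 and 3.3.1 report heart-rate changes in the single- and multiple-dose studies, and blood-pressure decreases at doses above those used here. SAP Table 2 defines orthostatic and supine potentially clinically significant (PCS) findings, but none of them gets a difference from placebo.

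**Working it through.** **The plan's own figures.** No sample size, power or precision is stated for safety. The figures in SAP section 8 concern the abdominal pain score only. With 60 per arm, a difference of 1.0, an SD of 1.9 and two-sided 0.05, the t-test power is 81.6%, which agrees with the stated 80% or more. The pooled comparison (180 v 60) computes to 94.0%, just under the stated 95%. Neither figure bears on safety.

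**Inputs.** 60 per arm (SAP section 8) and 95% two-sided intervals (SAP section 7.5). Event rates are my assumption, because the documents give none. All randomized subjects are assumed dosed, so that the Safety Set has 60 per arm.

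**Formula.** Newcombe's hybrid-score interval for d = p1 − p2, with Wilson limits (l, u) for each arm:

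- lower = d − √[(p1 − l1)² + (u2 − p2)²]
- upper = d + √[(u1 − p1)² + (p2 − l2)²]

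**Equal rates, 6/60 v 6/60.** The Wilson limits for 6/60 are 4.66% and 20.15%. The half-width is √[(10 − 4.66)² + (20.15 − 10)²] = √(28.5 + 103.0) = 11.5 points.

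**Unequal rates, 12/60 v 6/60.** The Wilson limits for 12/60 are 11.83% and 31.78%.

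- lower = 10 − √[(20 − 11.83)² + (20.15 − 10)²] = 10 − 13.0 = −3.0
- upper = 10 + √[(31.78 − 20)² + (10 − 4.66)²] = 10 + 12.9 = +22.9

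| Assumed events, olorinab v placebo | Difference (points) | 95% CI (points) |
|---|---|---|
| 0/60 v 0/60 | 0 | −6.0 to +6.0 |
| 3/60 v 3/60 | 0 | −9.3 to +9.3 |
| 6/60 v 6/60 | 0 | −11.5 to +11.5 |
| 12/60 v 12/60 | 0 | −14.3 to +14.3 |
| 30/60 v 30/60 | 0 | −17.3 to +17.3 |
| 12/60 v 6/60 | +10 | −3.0 to +22.9 |
| 18/180 v 6/60 (all doses pooled) | 0 | −10.8 to +7.5 |

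For 25 and 50 mg pooled (120 v 60) at 10% in both groups, the simple Wald half-width is 1.96 × √[0.1 × 0.9 × (1/120 + 1/60)] = 9.3 points. Pooling narrows the interval only modestly, because the placebo arm stays at 60.

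**How many intervals to ask for.** SAP section 19.1.9 has about 16 distinct categories and Table 2 has 13 rows. Against five olorinab groupings that is (16 + 13) × 5 = 145 intervals, of which about 145 × 0.05 ≈ 7 would exclude zero by chance if there were no true differences and coverage were exactly 95%. A short list of four adverse-event outcomes, three orthostatic findings and three mean differences at one visit gives (4 + 3 + 3) × 5 = 50 intervals, with 2 or 3 expected by chance on the same basis.

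**The case against.** The strongest reply is that the SAP does what the protocol's own safety section says. Protocol section 8.3.4 is descriptive, and SAP section 18.1.3 reserves hypothesis testing, and the definition of a met primary endpoint, for the pain score. Placebo is displayed beside every olorinab group, which is a descriptive comparison against a randomized control. Anyone with the counts and group sizes can work out a difference and interval. The endpoint itself contains no comparative wording; only the objective does. All of this stands, and it is why the point is an improvement and not an error. It does not remove the gap: differences derived afterwards are chosen afterwards, whereas a prespecified list fixes the outcomes and the method.

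A reader might go further and infer that SAP section 19 contradicts SAP section 9.4, or silently departs from protocol section 8.3 despite the statement in SAP section 4.3 that "There are no changes in analysis or definitions from those planned in the final protocol". The documents do not clearly support either inference. The sentence in section 9.4 says how pairwise estimates will be interpreted; it does not promise one for every primary endpoint. The modelling text in protocol section 8.3 adjusts for baseline pain score and so reads as efficacy text, while section 8.3.4 is the specific rule for safety.

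The exclusion in section 19 also covers only statistical comparisons and allows exceptions. None appears in the readable safety text, but the redacted pages and separate table shells cannot be checked.

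**Conclusion.** The point holds in a limited form. A primary objective worded as a comparison with placebo has no planned estimate of the difference and no planned statement of its precision in the readable SAP. Safety data are not left unreported, no planned analysis is invalid, and omitting safety p-values is conventional.

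The information not shown is material. Across assumed equal rates of 5% to 50%, a single dose against placebo leaves about ±9 to ±17 points unresolved. These widths are illustrative: they depend on the assumed rates and on 60 dosed subjects per arm, and fewer dosed subjects would widen them. The change is worth making because it is cheap and uses data already tabulated.

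**What to change.** Replace the sentence in Main Study SAP section 19 with text to this effect: no hypothesis tests will be made for safety data; risk differences against placebo with 95% CIs (Newcombe or Miettinen-Nurminen) will be shown for each dose, 25 and 50 mg pooled, and all olorinab pooled, for the outcomes listed below; all intervals are descriptive and unadjusted.

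- **Adverse events:** any TEAE, related TEAEs, serious TEAEs, and TEAEs leading to discontinuation of study treatment.
- **Vital signs:** the orthostatic systolic, diastolic and pulse PCS findings, overall and not by visit.
- **Means:** differences with 95% CIs for change from baseline in supine systolic and diastolic pressure and heart rate, at one visit named in advance (for example Week 12).

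No data collection, sample size or clinical procedure changes. The cost is one revised paragraph, some table columns and about 50 unadjusted intervals, a few of which may exclude zero by chance. The list should stay short; extending it to every category in section 19.1.9 and every row of Table 2 would bring the total to about 145.

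If the sponsor prefers to keep safety purely by arm, the lesser alternative is to state that the comparison in the objective is meant descriptively. That settles the wording but leaves the imprecision unshown.
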